7.2 Randomisation and Stratification

This is a multicentre, randomisation study and a centralised registration system will be used to assign patients to treatment groups (1:1 allocation; 402 patients in each group). Patients will be allocated to treatments using a minimisation algorithm. The factors used in the algorithm will be:

- High grade vs. Low Grade
- Treatment Centre
- Type of surgery intended

7.3 Analysis Plan

The primary analysis will be performed on the intention-to treat population. A full statistical analysis plan will be developed prior to any analysis being performed.

7.3.1 Primary Efficacy Analysis

The primary analysis will be performed on the intention to treat population. A full statistical analysis plan will be developed prior to any analysis being performed.

One year occurrence of seizure

The occurrence of seizures within one year of randomisation will be compared between the study arms. The odds ratio, associated 95% confidence intervals and 2-sided p-values associated with the comparison of the arm from a logistic regression model fitted to the

presence of a seizure within one year of randomisation will be given. The estimated absolute difference in seizure rate will be reported together with associated 95% confidence interval.

This is the primary comparison.

7.3.2 Secondary Efficacy Analysis

The secondary study measures are:

• Time to first seizure

The time to first seizure, within one year of randomisation, will be compared between the study arms using an accelerated failure time model. The acceleration factor and 2sided p-values associated with the comparison of the two study arms from the accelerated failure time model fitted to the timing of a seizure within one year of randomisation will be given.

- Time to first tonic clonic seizure
 The time to first tonic clonic seizure, within one year of randomisation, will be compared
 between the study arms using an accelerated failure time model. The acceleration
 factor and 2-sided p-values associated with the comparison of the two study arms from
 the accelerated failure time model fitted to the timing of a seizure within one year of
 randomisation will be given.
- Patient reported symptoms and adverse events Adverse events will be graded in accordance with CTCAE v5.0. The grade of the tabulated adverse events will be compared between the study arms using a Mann-Whitney U test (exact method).
- Mood, personality, fatigue and memory Mood, personality, fatigue and memory will be assessed through the Liverpool Adverse Events Profile (LAEP) questionnaire. Additionally depressive symptoms will be assessed in detail using the PHQ-9 data. The grade or prevalence of these symptoms will be compared between study arms using a Mann-Whitney U test (exact method).
- Progression Free Survival

Progression will be determined clinically based upon interpretation of MRI scans, clinical state of the patient and steroid dose. Where an MRI is used to determine progression the date of progression will be the date of the scan. If steroid dose is the primary factor in determining progression the date of progression will be the date the dose was started or increased. Where clinical state is used to determine progression the date of progression will be the date of determine progression the date of progression will be the date the dose was started or increased. Where clinical state is used to determine progression the date of progression will be the date of progression the date of progression will be the date of assessment.

Progression free survival will be calculated as the difference between date of progression and date of randomisation.

A Kaplan-Meier plot of progression free survival will be presented. The median progression free survival time for each study arm will be tabulated together with the

corresponding 80% confidence interval. The corresponding hazard ratio and 80% confidence interval and 2-sided p-value associated with the comparison of the treatment arms from the Cox model fitted to the data will be reported.

Overall Survival

A Kaplan-Meier plot of overall survival will be presented. The median overall survival time for each study arm will be tabulated together with the corresponding 80% confidence interval. The corresponding hazard ratio and 80% confidence interval and 2-sided p-value associated with the comparison of the treatment arms from the Cox model fitted to the data will be reported.

• Quality adjusted life years

Once QALYs have been calculated, these values will be presented for the two randomised group, as well as QALYs calculated with the incremental cost per QALY gained at 12 months. As the trial follow up period is 12 months, costs and effects will not be discounted.

These data will be analysed using both the trial data (unadjusted costs and effects) and regression analyses, specifically seemingly unrelated regression models [⁴⁰], which can simultaneously estimate both costs and health outcomes at the individual level whilst taking into account the fact that the contemporaneous error terms may be correlated. Statistical imprecision will be presented as confidence intervals around differences in effectiveness, cost and cost-effectiveness.

• Cost to the NHS and personal social services

Once mean costs have been calculated, these values will be presented for the two randomised group, as well as incremental mean costs calculated with the incremental cost per QALY gained at 12 months. As the trial follow up period is 12 months, costs and effects will not be discounted.

A within-trial economic analysis will estimate the incremental cost per quality adjusted life year (QALY) gained over a 12 month time horizon. The perspective of the analysis (i.e. whose costs and benefits are considered) will be the NHS and personal social services, but we will also take a wider perspective by including costs borne by trial participants, for example out of pocket expenses on health care and the time and travel costs of accessing care.

• Model costs, QALYs & incremental cost per QALY gained

The output of the economic model will be used to produce estimates of costs, effects, incremental costs, QALYs, and ultimately measure cost-utility. Cost-effectiveness will be reported as incremental cost per QALY gained over the patient's lifetime. As the duration of the model-based analysis is greater than one year, both costs and effects will be discounted at 3.5% in the base case analysis where appropriate, in line with current guidance from NICE [⁴¹].

To explore uncertainty in the model parameters such as variations in unit prices, and parameter statistical imprecision we will conduct extensive deterministic (e.g. for unit prices) and probabilistic (for statistical imprecision) sensitivity analyses. For the latter we will attach appropriate distributions to the model input parameters. This method

requires treating each input in the model as a distribution and using Monte Carlo simulation. The results from this analysis will be presented as plots of costs and QALYs derived from the probabilistic analysis and Cost-Effectiveness Analysis Curves.

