2. TRIAL OBJECTIVES

2.1. Study design

This is a two arm, multicentre, phase III randomised trial of prophylactic anti-epileptic drug (Levetiracetam) versus no anti-epileptic drug (AED) (comparator) in patients with suspected cerebral glioma.

2.2. Primary objective:

To determine 'In seizure-naive newly diagnosed cerebral glioma patients undergoing surgery, does prophylactic levetiracetam pre-operatively and for at least 1 year, produce a meaningful (>50%) reduction in the risk of developing seizures, when compared with standard care (No AED)?'

The Primary Outcome is one year risk of first seizure.

2.3. Secondary objectives:

- To determine whether prophylactic levetiracetam increases time to first seizure
- To determine whether prophylactic levetiracetam increases time to first tonic clonic seizure
- To determine whether prophylactic levetiracetam affects mood, personality, fatigue and memory
- To determine whether levetiracetam positively influences the severity of first seizure should it occur
- To determine whether levetiracetam impacts on quality of life
- To determine whether levetiracetam impacts on progression free survival.
- To determine whether levetiracetam impacts on overall survival
- To determine whether levetiracetam given prophylactically reduces costs to the NHS (National Health Service) and personal social services (PSS) over the 12 months trial follow-up.
- To determine the cost-effectiveness of prophylactic levetiracetam measured as incremental cost per QALY (quality adjusted life year) at 12 months and modelled over estimated survival.

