3.4. Randomisation

After ensuring that the patients meet **all** eligibility criteria and has consented to participate in the study, sites will randomise the patient following the instructions described in the 'SPRING work instructions for sites.

Once a patient has been randomised, a patient study number will be issued and this should be used in all correspondence.

Informed Consent/Authorisation

All Patients that are eligible to receive therapy and randomised to AED arm must undergo an Electrocardiogram (ECG) and pregnancy test (if female and of child bearing age) prior to starting trial medication. AED arm patients must initiate treatment prior to surgery and have taken a minimum of two doses of 500mg Levetiracetam (two doses of 250mg in CKD3 patients) prior to surgery. See Patient Pathway (Page 7).

Prior to protocol enrolment and initiation of treatment, subjects must sign and date an approved consent form.

Eligibility Exceptions

Eligibility exceptions will not be granted.

Withdrawal of Subjects

Patients *discontinue* from the study drug for reasons such as safety or non-compliance. These patients will continue to be followed up for efficacy and safety as per protocol, unless they are lost to follow up or deceased. Patients may *withdraw* from the study at any point and they do not have to give a reason. However, we will ask the patient's permission to continue to collect information on their progress that is routinely recorded in their medical records. This is so that the overall quality of the study is not impaired. The patient can say no at this point and then no further data collection will take place, and will be censored at the point of withdrawal. This should be indicated on the case report form (CRF) as per completion guidelines.

Patients who consent to the trial but do not undergo planned surgery will be withdrawn from the trial. For any patient that did not undergo planned surgery, a further patient would be enrolled to the trial to maintain the target number of patients for analysis.

Please note that should it be medically required, participants in either study arm will be removed from the study and treated with appropriate medication according to standard care.

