The median survival statistics and mortality by 1 year for each grade of cerebral glioma (Grade 2-4) have been taken from routine "standard of care" randomised control trial papers for treatment: Grade 4¹¹⁻¹⁴. There are no suitable trials in grade 1 cerebral glioma, but we anticipate there will be relatively few of these and therefore have included the percentage number of cases in with the frequency of grade 2 tumours (Table 5).

Table 5:

| Tumour Type | Proportion of study population | Median Survival(months) | Mortality by 1 year | Mortality as a % of population | Attrition due to mortality |
|------------------|--------------------------------------|----------------------------|------------------------|--------------------------------------|----------------------------------|
| Grade 4 (GBM) | 65% | 14.6 | 38.4% | 25.0% | 22.2% |
| Grade 3 | 20% | 39/57 | 10.0% | 2.0% | 1.8% |
| Grade 2 | 15% | 84 | 6.8% | 1.0% | 0.9% |
| Total | 100% | | | 28.0% | 24.8% |

We have estimated an attrition rate in this population of 24.8% due to mortality at 1 year

Attrition Rate drop-out due to Adverse Events

In general in epilepsy studies, treatment failure for unacceptable side-effects is largely limited

to the early post-randomisation period. We wish to gain the earliest effect, because of the risk of early seizures (up to 5% in first post-operative week) in cerebral glioma patients, but appreciate that early attrition could be a problem if there was drop out due to intolerable side effects. It is recognised that levetiracetam has fewer early adverse events due to rash or haematological toxicity and drug-drug interactions than first generation AEDs (phenytoin, carbamazepine) and lamotrigine.

In a systematic review of the literature around levetiracetam dose and drop outs from study - we have looked at:

- a) Dropout rates in RCT of levetiracetam vs. Carbamazepine for non-tumoural resistant epilepsy. (Staring dose 500mg bid and increased as necessary to 1.5gr bid). Withdrawal rates were 14.4% with levetiracetam and 19.2% with carbamazepine⁵.
- b) Dropout rate in RCT of intravenous levetiracetam vs. Phenytoin for prophylactic seizures after craniotomy) (levetiracetam 11% vs. Phenytoin 13% at 3months)⁶.

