7.3.4 Final Analysis

The Final Analysis will take place when all patients have been followed up for a minimum of one year following randomisation.

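### Progression free survival is calculated from a progression date only, so a death without dated progression is not an event and the planned analysis describes time to progression

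*Protocol*

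**What the plan says.** Section 2.3 lists the endpoint as its own secondary objective: "To determine whether levetiracetam impacts on progression free survival".

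Section 7.3.2 defines it in two steps. First, what counts as progression: "Progression will be determined clinically based upon interpretation of MRI scans, clinical state of the patient and steroid dose". Each of the three routes has its own date rule: the scan date, the date steroids were started or increased, or the assessment date. Second, the calculation: "Progression free survival will be calculated as the difference between date of progression and date of randomisation".

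The analysis follows in the same section: "A Kaplan-Meier plot of progression free survival will be presented". Medians and a hazard ratio are given with 80% confidence intervals, and for the test: "2-sided p-value associated with the comparison of the treatment arms from the Cox model fitted to the data will be reported".

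Death appears in neither step. The only censoring statement in the protocol is in section 3.4. It concerns patients who withdraw and refuse further data collection, who "will be censored at the point of withdrawal". Overall survival is a separate measure with its own analysis, so it does not bring death into this one.

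**The concern.** The objective and the label say progression free survival, in which death normally counts as a failure. The written formula counts progression alone. A patient who dies without a dated progression has no end date under that formula, so the analyst must either censor at the date of death or leave the patient without a value. In neither case is the death an event.

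This matters more here than in a low-mortality population, because section 7.1 expects roughly a quarter of patients to die within a year. Some deaths could also bear on the treatment question. Section 1.5 names status epilepticus, aspiration pneumonia and sudden unexpected death in epilepsy as possible consequences of seizures, and suggests that prophylaxis might prevent some of them. Such deaths are probably few, but the present rule could not register them. The stake is that a named secondary objective would be answered with a different quantity from the one stated.

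**Working it through.** **Inputs from the protocol**

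- Sample size 804, 402 per arm (section 7.1).
- One-year mortality: "We have estimated an attrition rate in this population of 24.8% due to mortality at 1 year" (section 7.1). Table 5 also gives a total of 28.0% as mortality in the population. Both are used below as a range.
- Follow-up: "The Final Analysis will take place when all patients have been followed up for a minimum of one year following randomisation" (section 7.3.4). Deaths by one year are therefore a lower bound for deaths at analysis, on the plan's own mortality.

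**The plan's own figures reproduce**

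- Table 5 mortality: 0.65 × 38.4% + 0.20 × 10.0% + 0.15 × 6.8% = 24.96% + 2.00% + 1.02% = 27.98%, stated as 28.0%.
- Sample size: 20% against 10%, two-sided 5%, 90% power, pooled variance and no continuity correction give 266 per arm, or 532. Then 532 / ((1 − 0.248) × (1 − 0.12)) = 803.9, rounded to 804. None of this depends on the definition at issue.

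**Deaths expected by one year**

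- 804 × 0.248 = 199.
- 804 × 0.280 = 225.

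**Events missed.** The protocol does not give the share of deaths without a prior dated progression. Assumed range: 10% to 40%.

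- 10%: 0.10 × 199 = 20, to 0.10 × 225 = 23.
- 40%: 0.40 × 199 = 80, to 0.40 × 225 = 90.
- Overall, about 20 to 90.

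**Effect on the Kaplan-Meier estimate (illustration).** Assume constant hazards, a true median of 10 months, and a share s of first events that are deaths. With deaths censored, the median becomes 10 / (1 − s), and the one-year event-free proportion becomes exp(−(ln 2 / 10) × 12 × (1 − s)).

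| s | Median (months) | Event-free at one year |
|---|---|---|
| 0 (true) | 10.0 | 43.5% |
| 10% | 11.1 | 47.3% |
| 20% | 12.5 | 51.4% |
| 30% | 14.3 | 55.9% |

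If such patients are instead left out, the one-year proportion is still too high, because failures leave the denominator. At s = 20%, of the 56.5% who fail by one year, 0.20 × 56.5% = 11.3% are deaths. The estimate is 43.5 / (100 − 11.3) = 49.0% against the true 43.5%.

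**Effect on the hazard ratio (illustration).** With s the share of deaths in the control arm, the composite hazard ratio is (1 − s) × HR for progression + s × HR for death without progression. Take s = 20% and a progression hazard ratio of 1.0.

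- Death hazard ratio 0.7: 0.8 + 0.2 × 0.7 = 0.94.
- Death hazard ratio 1.3: 0.8 + 0.2 × 1.3 = 1.06.

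An analysis that censors deaths estimates 1.0 in both cases. That value is correct for progression, but it is not the hazard ratio for progression free survival.

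**The case against.** The strongest reply is that the sentence only fixes the origin and end date for patients who progress, that the word survival in the label already implies death, and that the protocol defers a full statistical analysis plan, where event and censoring rules are usually set. The protocol is equally brief about overall survival, which suggests economy of wording and not a decision to exclude deaths. This does not remove the point. The protocol writes out a formula and lists the qualifying routes, so an analysis plan that counted death would have to depart from the written rule.

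Other parts of the reply stand, and they rule out stronger readings that a reader might infer:

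- *That the plan censors deaths.* It does not say so. Censoring is one of two ways to apply the formula; having no value is the other.
- *That undated deaths are likely because the visit table shows no MRI at 6, 9 or 12 months.* Clinical state and steroid dose each suffice. Neurological examination and concomitant medications are recorded every three months. The table appears to mark MRI as standard care, so it need not show every scan.
- *That the hazard ratio will favour the arm with more deaths without progression.* A Cox model that censors deaths estimates the cause-specific hazard ratio for progression, which does not shift automatically when deaths differ by arm.

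**Conclusion.** The definition is wrong as written: followed literally, it yields time to progression under the name of progression free survival. That conclusion rests on the text alone.

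The size is less certain. The 199 to 225 deaths follow from the protocol's own mortality figures, but the 20 to 90 missed events rest on an assumed share of 10% to 40%. The shifts in median and hazard ratio rest on assumed constant hazards, an assumed median and assumed death shares. They show direction and order of magnitude and do not predict this trial's result.

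Severity is moderate. A reader might take this as a threat to the trial's main conclusion, but the documents do not support that. The primary outcome is seizure within one year, the endpoint at issue is one of nine secondary objectives with no stated power, and overall survival is analysed separately, so a mortality difference would still be reported.

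**What to change.** Replace the calculation sentence in section 7.3.2 with a definition of progression free survival as the time from randomisation to the earlier of progression (by the three routes already listed) or death from any cause. State that patients alive and progression-free are censored at their last disease assessment. If time to progression is also of interest, report it separately under that name with death as a competing event.

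The cost is one sentence in the protocol, carried into the analysis plan. No new data are needed: section 4.2 follows all patients for overall survival, and section 6.1 collects survival and recurrence details. The sample size does not change.

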| | [name] |
| | [name] |
| | Email: [contact] |
| | |
| Patient | [name] |
| representative | Brains trust |
| | [name] |
| | [name] |
| | [name] |
| | [name] |
| | Email: [contact] |
| | Email. [contact] |

Synopsis

Protocol ID: SPRING

Protocol Title: Seizure PRophylaxis IN Glioma

Trial Description: A phase III randomised trial comparing prophylactic levetiracetam versus no prophylactic anti epileptic drug in patients with newly diagnosed presumed supratentorial (cerebral) glioma.

Development Phase: Randomised phase III

Primary Objective: To determine 'In seizure-naive newly diagnosed cerebral glioma patients undergoing surgery, does prophylactic levetiracetam preoperatively and for at least 1 year, produce a meaningful (>50%) reduction in the risk of developing seizures, when compared with standard care (No AED)?'

The Primary Outcome is one year risk of first seizure.

Secondary Objectives:

- To determine whether prophylactic levetiracetam increases time to first seizure.
- To determine whether prophylactic levetiracetam increases time to first tonic-clonic seizure.
- To determine whether prophylactic levetiracetam affects mood, personality, fatigue and memory.
- To determine whether levetiracetam positively influences the severity of first seizure should it occur.
- To determine whether levetiracetam impacts on quality of life.
- To determine whether levetiracetam impacts on progression free survival.
- To determine whether levetiracetam impacts on overall survival.
- To determine whether levetiracetam given prophylactically reduces costs to the NHS and personal social services (PSS) over the 12 months trial follow-up.
- To determine the cost-effectiveness of prophylactic levetiracetam measured as incremental cost per QALY at 12 months and modelled over estimated survival.
- Study Design: Two arm, multicentre phase III randomised trial of prophylactic antiepileptic drug (Levetiracetam) versus no anti-epileptic drug (AED) (comparator) in patients with suspected cerebral glioma. Randomly assigned - 1:1 basis. Patients will be followed up for 12 months. The trial will end when the last living patient has completed their 12 month follow up visit.

| Patient Accrual: | 804 patients will be recruited over a three-year period at sites in the UK. |
|-------------------|---|

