7. STATISTICS

7.1. Sample Size

Estimate of 1 year seizure rate in patients with suspected cerebral glioma after surgery is 20%. We anticipate a reduction in seizure rate to 10% in the treatment arm. Based on a 90% power to identify an improvement in 1 year seizure rate in the treatment arm compared to the control arm, this requires 532 patients across the two arms with a two-sided type I error level of 5%. Assuming a 24.8% 1 year mortality rate and that 12% of patients will be lost to follow-up, the final (maximum) sample size is 402 per arm.

Patients will be randomly assigned at a 1:1 ratio to the following groups:

• **Group 1**: Levetiracetam 500mg twice daily for 2 weeks, then increasing to 750mg twice daily thereafter for 1 year. Patients should have a minimum of 2 doses of 500mg prior to surgery. In those with moderate chronic kidney disease (eGFR 30-59 mL/min/1.73

m2) a starting dose of one 250mg twice a day for 2 weeks, then increasing to 500mg twice a day thereafter).

• **Group 2**: no AED treatment (standard care)

We anticipate an initial 6 month start up period, recruitment over 3 years, 1 year follow-up period and a further 9 months for data cleaning, analysis and report writing (total 65 months).

Conservative estimate of 1 year seizure rate in patients with suspected cerebral glioma after surgery is 20%. Based on the effect of levetiracetam of reducing seizure in patients with epilepsy we anticipate a reduction in seizure frequency to 10% in group 1.

Attrition due to limited Life Expectancy

The proportion of expected participants have been taken from the recognised potential frequency of cerebral glioma (low grade (Grade 1-2)/ high grade (Grade 3-4)¹¹⁻¹⁴. There will be a smaller proportion of high-grade cerebral glioma, as a higher proportion of grade 4 (Glioblastoma Multiforme) have a poorer performance status, which may preclude entry into

the study. However, more cases with grade 1 and grade 2 tumours will present with seizures, therefore will not be suitable for this study. On balance, we think that the proportion of cases with each grade are justifiable and are likely to represent the proportion recruited who would be at risk of first seizure.

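### PFS and OS are fixed at unexplained 80% confidence intervals beside two-sided p-values, against 95% for the primary outcome; and if OS is cut at 12 months its median will not be reached

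*Protocol*

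**What the plan says.** **Interval level.** Protocol section 7.3.2 gives PFS and OS the same treatment: a Kaplan-Meier plot, a median per arm, and a Cox model. For OS, "The median overall survival time for each study arm will be tabulated together with the corresponding 80% confidence interval". The Cox result for each outcome is described as "The corresponding hazard ratio and 80% confidence interval and 2-sided p-value associated with the comparison of the treatment arms from the Cox model". The 80% level therefore appears four times, once for the median and once for the hazard ratio of each outcome.

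For the primary outcome, section 7.3.1 specifies "The odds ratio, associated 95% confidence intervals and 2-sided p-values". Section 7.1 states that "this requires 532 patients across the two arms with a two-sided type I error level of 5" percent. Both PFS and OS are listed secondary objectives (Synopsis and section 2.3), worded as determining whether levetiracetam has an impact on them. Nothing in the protocol explains 80% or labels these two outcomes exploratory.

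**Length of survival follow-up.** The statements differ:
- The Synopsis says patients are followed for 12 months and "The trial will end when the last living patient has completed their 12 month follow up visit". The QALY and cost items of section 7.3.2 also call the trial follow-up period 12 months.
- Section 4.2 says all patients are followed for overall survival and gives no end date.
- The footnote to the visit schedule (section 4.3) gives at least one year, with 18-month data where possible. The 18-month column itself lists only AED details.
- Section 7.3.4 makes one year a minimum at the final analysis.

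**The concern.** A reader of the trial report will see 95% intervals for seizures and 80% intervals for survival, each beside a two-sided p-value. The usual reading is that an interval excluding 1 signals an effect. At 80% that reading corresponds to p below 0.20, while the trial's own level is 5%. PFS and OS are the outcomes where this matters most, because section 1.5 cites evidence that levetiracetam may inhibit glioma-cell proliferation and increase sensitivity to temozolomide. A survival signal will therefore be looked for.

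This is not a detail left for the SAP, since the protocol itself fixes the level.

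The second matter is the OS median. If OS is censored at 12 months, the protocol's own mortality assumptions put that median beyond the data.

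**Working it through.** **Inputs.** Section 7.1: 1-year seizure rates of 20% (control) and 10% (levetiracetam); 90% power; two-sided 5%; 804 patients, 402 per arm. Table 5: grade 4 is 65% of patients, median 14.6 months, 1-year mortality 38.4%; grade 3 is 20%, 39/57 months, 10.0%; grade 2 is 15%, 84 months, 6.8%.

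**1. The plan's own figures.** Pooled two-proportion formula: n per arm = [1.960·√(2·0.15·0.85) + 1.282·√(0.2·0.8 + 0.1·0.9)]² / 0.10² = 265.9, so 266 per arm and 532 in all, as stated. Inflation: 532/((1 − 0.248)(1 − 0.12)) = 803.9, so 804. Table 5 total: 0.65·0.384 + 0.20·0.100 + 0.15·0.068 = 0.2798, or 28.0%, as stated. The two-sided 5% level is thus the one that sized the trial.

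**2. Width.** The multipliers are 1.282 (80%) and 1.960 (95%). The ratio is 1.282/1.960 = 0.654, so the 80% interval is about 65% as wide on the log hazard-ratio scale.

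**3. Where interval and 5% level part.** Expected deaths by one year: 0.28 × 804 ≈ 225. With 1:1 allocation, SE(log HR) ≈ 2/√225 = 0.133.
- The 80% interval excludes 1 when HR < exp(−1.282·0.133) = 0.84 or HR > 1.19.
- p < 0.05 when HR < exp(−1.960·0.133) = 0.77 or HR > 1.30.
- Between these bounds, 0.77 to 0.84 and 1.19 to 1.30, the interval excludes 1 while p exceeds 0.05.
- Example: an observed HR of 0.80 gives log HR −0.223, z = 1.67, p ≈ 0.09, 80% interval 0.67 to 0.95, 95% interval 0.62 to 1.04.

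With the 24.8% mortality figure instead (about 199 deaths), the null-centred intervals are 0.83 to 1.20 (80%) and 0.76 to 1.32 (95%), which gives the same picture.

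Under no effect, the 80% interval excludes 1 in 20% of trials; in 20% − 5% = 15% it does so with p between 0.05 and 0.20.

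**4. Median OS if censored at 12 months.** Expected mortality is 28.0%, so about 72% are alive and the median is not reached. Grade 4 alone, at 38.4%, does not reach it either. Beyond 12 months an assumption about curve shape is needed:

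| Assumption for each grade | Alive at 18 months | Median of the mixture |
|---|---|---|
| Exponential from Table 5 medians | 55–57% | 21–23 months |
| Exponential from Table 5 one-year mortality | 62% | 27 months |
| Weibull through both columns | 53–54% | 19 months |

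An 18-month cut would not be expected to reach the median on any of these.

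**5. Median OS if followed to the end of the trial.** With uniform accrual over 36 months and a close at 48 months, the share with potential follow-up beyond t months is (48 − t)/36: 81% at 19, 75% at 21 and 58% at 27 months. With the staggered site openings under Table 6, the shares are lower, about 31% to 68%, depending on the median and closing month. The Kaplan-Meier median could then be estimated.

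The protocol gives no progression rate, so the same check cannot be made for the PFS median.

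**The case against.** A correctly labelled 80% interval is valid: it covers at 80% and agrees exactly with p below 0.20. The p-value is printed beside it and no decision rule is attached. That stands. The defect is an unexplained change of level within one report and the misreading it invites, not an invalid interval.

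A reader might infer that the OS summary cannot be estimated. The documents do not support this. The Kaplan-Meier plot and Cox hazard ratio are planned and estimable on either reading, with about 200 to 225 deaths by one year. Only the median is in question, and only if OS is cut at 12 (or 18) months. Sections 4.2, 4.3 and 7.3.4 leave room for longer follow-up, and section 10.1 provides for tracing through national records. Nor would a median with follow-up to trial end rest on a handful of early patients, as step 5 shows.

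A reader might also infer that chance differences will probably look like survival effects. The rate under no effect is 20% per outcome. A joint rate of 36% (1 − 0.8²) would need PFS and OS to be independent, which is implausible in the same patients.

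Finally, reporting the median only if reached could be left to the SAP. That is fair as a detail, but the protocol's differing follow-up statements still need to be reconciled.

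**Conclusion.** The interval-level point holds. The protocol fixes 80% for the medians and hazard ratios of two stated secondary objectives, gives no reason, and departs from its own 95% intervals and two-sided 5% level. Its size is an interval 65% as wide as the 95% one, and a band of observed hazard ratios (about 0.77 to 0.84 and 1.19 to 1.30) where interval and 5% level point different ways. That band rests on about 225 deaths, from Table 5 applied to all 804 patients, and the usual approximation for the standard error.

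The OS-median point holds conditionally. At a 12-month cut the median is not expected to be reached on Table 5 alone. At 18 months this also depends on the assumed curve shape. With follow-up to trial end it may well be reached.

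Neither point touches the primary analysis or the sample size.

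**What to change.** 1. In section 7.3.2, replace 80% by 95% in all four places: the PFS and OS medians and the PFS and OS hazard ratios.
2. Reconcile the follow-up statements in the Synopsis and sections 4.2, 4.3, 7.3.2 and 7.3.4, and state the censoring date for OS.
3. If OS is censored at 12 months, report the 12-month Kaplan-Meier survival in each arm and its difference with a 95% confidence interval, and give the median only if reached. Keep the Kaplan-Meier plot and Cox hazard ratio.

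The cost is wording. No patients or visits are added, and the only statistical downside is that the reported intervals become wider.
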